## **5.7. Criteria for Study Pausing or Termination**

The Sponsor reserves the right to discontinue the study at any time for any reason. Such reasons may be any of, but not limited to, the following:

- Occurrence of AEs unknown to date in respect to their nature, severity, and duration, or the unexpected incidence of known AEs
- Any SAE pending review by the Safety Review Committee (SRC)
- Two Grade 3 or one Grade 4 AE pending review by the Safety Review Committee (SRC)
- Any death pending review by the Safety Review Committee (SRC)
- Medical or ethical reasons affecting the continued performance of the study

If the study is prematurely terminated, the Investigator is to promptly inform the study subjects and Independent Ethics Committee (IEC) and should ensure appropriate follow up for the subjects. All procedures and requirements pertaining to the archiving of study documents should be followed. All other study materials (e.g., study drug, etc.) must be destroyed or returned to the Sponsor.

## **6. STUDY POPULATION**

### **6.1. Number of Subjects**

A total of 32 (6 rhu-pGSN and 2 placebo recipients per dose cohort x 4 dosing levels).

### **6.2. Subject Inclusion Criteria**

1. Healthy male or female adults 18 to 50 years of age without chronic or active acute medical conditions
2. Informed consent obtained from subject
3. Weight <100 kg and body mass index (BMI) <25 kg/m^2
4. Willingness during the course of the study, starting at screening and for at least 3 months after their final study treatment:
  - a) Female subjects of childbearing potential must agree to use 2 medically accepted/Food and Drug Association (FDA)-approved birth control methods
  - b) Male subjects with a partner who might become pregnant must agree to use reliable forms of contraception (i.e., condom, vasectomy, abstinence), or an acceptable method of birth control must be used by the partner
  - c) All subjects must agree not to donate sperm or eggs

### **6.3. Subject Exclusion Criteria**

1. Pregnant or lactating women
2. Acute illness during the month prior to screening
3. Circumstances that may require any medications (including prescription medication, over-the-counter medication, vitamins, or supplements) during the conduct of the study other than acetaminophen
4. Hospitalization during the year prior to screening
5. History of cancer or treatment with systemic chemotherapy or radiation therapy at any time
6. Transplantation of hematopoietic or solid organs
7. History of diabetes mellitus; myocardial infarction, angina, or other cardiovascular disease; stroke or cerebrovascular disease; chronic obstructive pulmonary disease (COPD) or asthma; deep vein thrombosis (DVT)/pulmonary embolism (PE); liver or kidney disease; psychiatric condition; or active or chronic infection
8. Receipt of blood products during the year prior to screening
9. Chronic mechanical ventilation or dialysis
10. Any clinically significant abnormalities in clinical chemistry, hematology, or urinalysis results as judged by the Investigator

11. Any clinically significant abnormalities of vital signs or physical examination findings as judged by the Investigator
12. Positive results for recreational drugs during screening
13. Any other condition deemed by the Investigator as possibly interfering with the conduct of the study

#### **6.4. Subjects or Partners of Subjects of Reproductive Potential**

Pregnancy is an exclusion criterion and women of childbearing potential must not be considering getting pregnant during the study. Unless they have had a hysterectomy, female subjects must have a negative serum or urine pregnancy test within 36 hours prior to start of study drug. A serum or urine pregnancy test will be performed at the EOS Visit. A total of 2 acceptable methods of birth control must be used per couple.

Women of childbearing potential must practice 2 acceptable methods of birth control starting at screening and continuing at least 3 months after the last study treatment. Acceptable methods of birth control in this study include true sexual abstinence (i.e., completely refraining from heterosexual intercourse throughout the study), hormonal methods (e.g., “the pill,” hormone injections, implants), barrier methods (e.g., condom or diaphragm), intrauterine device (IUD or “coil”), or sex exclusively with a sterilized partner. An accepted birth control method used by the male partner can count as one of the 2 acceptable methods of birth control for the woman.

Male subjects with a partner who might become pregnant must use reliable forms of contraception (i.e., condom, vasectomy, abstinence) during the study starting at screening and for at least 3 months after the last study treatment, and an acceptable method of birth control must be used by the female partner (i.e., oral contraceptive, IUD, hormonal implants, contraceptive injection, or a double-barrier method).

Subjects will be instructed to notify the Investigator if pregnancy is discovered either during or within 3 months of the last dose of study drug.

#### **6.5. Waivers of Inclusion/Exclusion Criteria**

No waivers of these inclusion or exclusion criteria ([Section 6.2](#) and [Section 6.3](#)) will be granted by the Investigator and/or the Sponsor or its designee for any subject enrolling into the study.

## 7. DESCRIPTION OF STUDY TREATMENT

### 7.1. Description of Study Drug

Rhu-pGSN drug product is provided as lyophilized powder containing rhu-pGSN plus excipients. It is provided in 10-mL glass vials to be reconstituted to a volume of 5.3 mL with 4.9 mL of sterile water yielding a final concentration of 40 mg/mL of rhu-pGSN, 2% glycine, 4% trehalose, 0.5% arginine, and 0.1% poloxamer 188 in a 10-mM phosphate buffer, pH 7 (Table 3).

Rhu-pGSN is administered via IV push  $\leq$ 20 mL/minute. A total of 5 doses of rhu-pGSN will be administered to participating subjects at 0, 12, 36, 60, and 84 hours (Dose 1 is administered at time 0; a window of  $\pm$ 2 hours will be allowed around dosing times for the 2nd and 3rd doses, and  $\pm$ 4 hours for the last 2 doses).

**Table 3: Investigational Product**

	Investigational Product
Product Name:	rhu-pGSN
Dosage Form:	Powder for solution filled as a 5.3 mL fill in 10 mL glass vials
Unit Dose	rhu-pGSN reconstituted to a volume of 5.3 mL with 4.9 mL of sterile water
Route of Administration	Intravenous
Physical Description	Lyophilized powder
Storage Conditions	2 to 8 °C
Manufacturer	Drug Product: Lyophilization Services of New England, Inc., [name]

Vials containing rhu-pGSN study drug will be labeled according to national regulations for investigational products.

### 7.2. Description of Placebo

Placebo will be dosed at a weight-based volume of  $0.025 \text{ mL/mg} \times \text{dose in mg/kg} \times \text{weight in kg}$  of 0.9% saline solution via IV push (matching the volume of rhu-pGSN for a subject of that size) injected at  $\leq$ 20 mL/minute through a standard 0.2  $\mu$  filter at 0, 12, 36, 60, and 84 hours (Dose 1 is administered at time 0; a window of  $\pm$ 2 hours will be allowed around dosing times for the 2nd and 3rd doses, and  $\pm$ 4 hours for the last 2 doses). The placebo requires no special manipulation.

### **7.3. Preparation of Study Drug for Administration**

The Investigator or designee will be responsible for administering the appropriate dose of IV rhu-pGSN to subjects. rhu-pGSN must be stored refrigerated at 2 to 8 °C in its original package in an appropriate storage facility accessible only to the pharmacist(s), the Investigator, or a duly designated person.

The unblinded pharmacist will determine the dose (mg) of rhu-pGSN, calculate the volume of rhu-pGSN solution needed, and reconstitute lyophilized study drug with sterile water.

The individual rhu-pGSN infusion will be prepared under aseptic conditions and administered at the study site according to the directions of the Sponsor, which will be provided in a Pharmacy Manual. Any powder remaining in the vial must be discarded. After dilution for infusion, administration of rhu-pGSN should be initiated as soon as possible but no later than 6 hours. Maximum allowed storage times and conditions will be detailed in the Pharmacy Manual.

### **7.4. Study Drug Administration**

rhu-pGSN is administered via IV push  $\leq$ 20 mL/minute. A total of 5 doses of rhu-pGSN will be administered to participating subjects at 0, 12, 36, 60, and 84 hours. Dose 1 is time 0; a window of  $\pm$ 2 hours will be allowed around dosing times for the 2nd and 3rd doses, and  $\pm$ 4 hours for the last 2 doses.

Subjects are to be monitored for administration site reactions during an infusion and for 1 hour after its completion. Infusion site reactions will be recorded as AEs using the appropriate coding terms on the eCRF.

### **7.5. Subject Monitoring During rhu-pGSN Infusion**

Vital signs should be measured as outlined in [Section 8.1.3](#). All supportive measures consistent with optimal patient care will be provided throughout the study according to institution standards.

Precautions for anaphylaxis should be observed during rhu-pGSN administration. Emergency resuscitation equipment and medications should be readily available. Additional supportive measures should also be available and may include, but are not limited to, epinephrine, antihistamines, corticosteroids, IV fluids, vasopressors, oxygen, bronchodilators, diphenhydramine, and acetaminophen (paracetamol).

### **7.6. Shipment of Study Drug**

Prior to study treatment, study medications will be supplied to the clinical trial site's pharmacy by the Sponsor or its designee.

Shipment of study drug supplies for the study will be accompanied by a shipment form describing the contents of the shipment, drug information, and other appropriate documentation. The shipment form will assist in maintaining current and accurate inventory records.

## **7.7. Receipt and Storage of Study Drug**

All study supplies should arrive at the pharmacy in sufficient quantity and in time to enable dosing as scheduled. The Investigator must ensure the acknowledgement of receipt of the clinical trial material (i.e., study drug and placebo) at the site, including that the material was received in good condition.

The Sponsor or its designee must notify the Investigator/study staff prior to dispatch of drug supplies, with the anticipated date of their arrival, addressed to the site's pharmacy.

The investigational drug will be stored in the pharmacy, refrigerated at 2 to 8 °C. The Sponsor should be notified for any deviation from the storage conditions.

## **7.8. Accountability, Handling, and Disposal of Study Drug**

The study site must maintain accurate records documenting dates and amount of study drug received. The trial site's pharmacy will be responsible for ensuring the supervision of the storage and allocation of these supplies. When a shipment is received, the pharmacist will verify the quantities received and the accompanying documentation and will provide acknowledgment of receipt.

Accountability logs will be provided to assist the pharmacist in maintaining current and accurate inventory records covering receipt, dispensing, and disposition of the study drug. An unblinded study monitor will examine inventory during the study. Accountability records must be readily available and may be subject to inspection by regulatory authorities or independent auditors at any time.

Drug administration will be recorded in source documents and in the eCRFs.

At the end of the study, delivery records of study drug will be reconciled with used / unused supplies. A disposition form will be completed to verify that all used, unused or partially used supplies have been returned or destroyed following appropriate accountability review by the monitor. One copy of all accountability records and the disposition form will be retained by the Investigator for the study files.

## **7.9. Concomitant Medications**

Medications (i.e., prescriptions, over-the-counter medications, vitamins, or supplements) taken in the 6 weeks prior to study enrollment should be recorded and include the generic name (if possible). If known, document the start/stop date of each medication in the subject's file and in the eCRF.

During the study, no medications except acetaminophen are permitted.

## **7.10. Treatment Compliance**

The study drug will be administered by personnel at the study site to ensure compliance.

## **7.11. Randomization and Blinding**

Following screening, subjects qualified for study entry will be randomized to receive rhu-pGSN or placebo during the treatment period. All eligible subjects will be assigned a randomization number.

The investigational site team and the subject will be kept blinded to the treatment allocation of each participant. Only the designated pharmacist(s) will be unblinded to the treatment allocation. The unblinded pharmacist will randomly assign a treatment allocation.

### **7.11.1. Unblinding**

There is no antidote for rhu-pGSN. Unblinding should only be performed if knowledge of the treatment assignment will change the planned management of a medical condition. If possible, prior to unblinding, the need to unblind should be discussed with the Medical Monitor and Sponsor's Chief Medical Officer; however, this should not delay unblinding if the Investigator believes it is necessary. Each case of unblinding will be documented and documentation will be stored separately by the unblinded pharmacist.

Subjects that are unblinded may be withdrawn from the study. The decision to withdraw a subject from the study because of unblinding should be discussed with the Sponsor. If the subject is withdrawn, the Investigator or designee must record the date and reason for withdrawal on the appropriate eCRF for that subject.

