### **5.6. Criteria for Treatment Discontinuation**

Subjects are free to discontinue their participation in the study at any time and without prejudice to further treatment. The Investigator must withdraw any subject from the study if that subject requests to be withdrawn, or if it is determined that continuing in the study would result in a significant safety risk to the subject.

The subject's participation in this study may be discontinued for the following reasons:

- Any SAE
- Grade 3 AEs or Grade 4 AE
- Subject withdrew consent
- Subject is unwilling or unable to continue the study or is lost to follow up
- Subject is non-compliant with study procedures/study protocol

- Investigator decides that withdrawal from the study is in the best interest of the subject
- Any clinically significant change in subject's medical condition (at the discretion of the Investigator)
- Sponsor decision to end the study

If a subject withdraws from the study prematurely, assessments scheduled for the EOS Visit should be performed as soon as possible. If a subject refuses further assessment, the subject should be contacted for safety evaluations (AE/concomitant medications/potential pregnancy) approximately 28 days after study withdrawal.

If such withdrawal occurs, or if the subject refuses to participate in the EOS Visit, the Investigator must determine the primary reason for a subject's withdrawal from the study and record the information on the electronic case report form (eCRF). If the reason for withdrawal is an AE, monitoring should continue until the outcome is evident. The specific event or test result(s) must be recorded in the eCRF. At the discretion of the Sponsor, subjects may also be removed from the study ([Section 5.4](#)).

It should be clearly documented in the source data whether a subject withdrew his/her consent and will not enter the follow-up phase, or if a subject withdrew his/her consent for study drug treatment but will continue further participation in the study.

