## **9.7. Reporting Adverse Events**

All AEs, serious and nonserious, will be fully documented on the appropriate eCRF. For each AE, the Investigator must provide its duration (start and end dates or ongoing), intensity,

assessment of causality and whether specific action or therapy was required. All AEs occurring during this healthy-volunteer study will be presumed to be related to study drug unless occurring before the study therapy is initiated pending review by the SRC.

All AEs that occur from the signing of the informed consent form (ICF) until the first dose of study drug should be recorded on the AE eCRF page only if the event was related to a study procedure. All other AEs/findings prior to the first dose of study drug should be recorded as medical history on the applicable eCRF page. All AEs occurring from the first dose of study drug until 28 days after the last dose of study drug must be recorded on the AE eCRF.

All SAEs and Grade 4 AEs must be reported to the Sponsor within 24 hours of the Investigator's knowledge. All AEs occurring during this healthy-volunteer study will be presumed to be related to study drug unless occurring before the study therapy is initiated pending review by the SRC. This reporting should be done by faxing/emailing the completed SAE Report Form to the number provided on the SAE Report Form. After the EOS Visit, only new treatment-related SAEs need to be captured on the AE eCRF and reported to the Sponsor.

Investigators must follow subjects with AEs/SAEs until the event has resolved, the condition has stabilized, withdrawal of consent, the subject is lost to follow up or death OR until the EOS Visit, whichever occurs first. New and ongoing treatment-related SAEs should be followed beyond the EOS Visit. If the subject dies, this should be captured as the outcome of the AE unless no link between the AE and the subject death can be established, in which case the AE will be marked as ongoing and the death will be reported as a separate event.

If a subject is lost to follow up, this should be captured accordingly within the AE eCRF and on the follow up SAE report.

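### Section 7.11.1 lets a subject be withdrawn from the study because of unblinding, without securing the remaining scheduled safety follow-up through Day 28

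*Combined protocol and SAP*

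**What the plan says.** Section 7.11.1 sets the condition for breaking the blind in an individual subject: "Unblinding should only be performed if knowledge of the treatment assignment will change the planned management of a medical condition". It continues: "Subjects that are unblinded may be withdrawn from the study". The object of that sentence is the study, not only study treatment. The one control is consultation: "The decision to withdraw a subject from the study because of unblinding should be discussed with the Sponsor". No criteria are given. If the subject is withdrawn, the date and reason go on the eCRF.

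Other sections govern what happens after a withdrawal:

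- **Section 5.6:** "If a subject withdraws from the study prematurely, assessments scheduled for the EOS Visit should be performed as soon as possible". It also says "If a subject refuses further assessment, the subject should be contacted for safety evaluations", at about 28 days after withdrawal, and "If the reason for withdrawal is an AE, monitoring should continue until the outcome is evident".
- **Section 9.6:** AEs and clinically significant laboratory abnormalities are evaluated until values return to baseline or fit the subject's current condition.
- **Section 9.7:** "All AEs occurring from the first dose of study drug until 28 days after the last dose of study drug must be recorded". Follow-up of AEs and SAEs runs to resolution, stabilization or another listed end, "OR until the EOS Visit, whichever occurs first". Treatment-related SAEs are followed beyond EOS.
- **Section 10.3:** every subject given at least part of one dose stays in the full analysis set, and missing data are not imputed.

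**The concern.** The primary endpoint is the incidence and severity of AEs. Under 7.11.1 a subject reaches individual unblinding through a medical condition, so withdrawal because of unblinding depends on outcome. The choice is made after at least the investigator may know the allocation, and no criterion guides it. Nothing about knowing the arm makes later AEs, laboratory values or antibody results uninterpretable. The permission therefore gives up data and gains nothing in return.

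The cohorts are small. Each treated subject is 1 of 6 (16.7%) at a dose level, and no dropout allowance is stated. Because the analysis keeps the subject in the denominator and imputes nothing, a later event that was never collected would be counted as no event.

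**Working it through.** **1. What survives a withdrawal for unblinding.** Setting the sections side by side:

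| Data | Provision | Position if the recorded reason is unblinding |
|---|---|---|
| The event that led to unblinding | 9.7: recording of all AEs from first dose | Should be recorded |
| Its course to outcome | 5.6: monitoring, if the reason for withdrawal is an AE | May not apply; unblinding is not in the list of reasons in 5.6, and 7.11.1 does not refer to 5.6 |
| Its course to outcome | 9.6 and 9.7 | 9.6 points to continued evaluation; 9.7 stops at EOS except for treatment-related SAEs |
| New later events | 9.7: recording to 28 days after last dose | Required with no exception, but once EOS assessments are done early no further visit is scheduled; the contact in 5.6 is worded only for those who refuse assessment |
| Day 7 and Day 28 safety laboratory tests | Table 4 | Can be replaced by one early EOS draw |
| Day 28 antibody sample | Table 4; secondary endpoint in 4.2.2 | Can be replaced by an early sample, which does not measure the Day 28 endpoint |

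Table 4 schedules safety laboratory tests after dosing on Days 7 and 28 only. Under Section 5.2 the Safety Review Committee uses data through the Day 7 visit, laboratory tests included, to decide on the next cohort. A withdrawal during the inpatient days can thus remove a Day 7 result that this decision would have used. A withdrawal after Day 7 puts only the Day 28 items at risk.

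Section 5.6 separates stopping study drug from leaving the study, but only for withdrawal of consent. Section 7.11.1 does not make that distinction.

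**2. The plan's own figures.** Table 5 gives the true AE rate at which n subjects have a 90% probability of showing at least one event. The probability is 1 − (1 − p)^n, and the exact rate is p = 1 − 0.1^(1/n).

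| n | Table 5 rate | Probability at that rate | Exact 90% rate |
|---|---|---|---|
| 6 | 32% | 0.901 | 31.9% |
| 8 | 25% | 0.900 | 25.0% |
| 12 | 18% | 0.908 | 17.5% |
| 18 | 13% | 0.918 | 12.0% |
| 24 | 10% | 0.920 | 9.15% |

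Table 5 is reproduced, allowing for rounding of the rates. The exact rate is also the one-sided 90% upper limit when no event is seen.

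**3. One treated subject lost.** This is an assumption, not a forecast: one treated subject contributes nothing for some event type that would arise after the withdrawal.

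- One dose level: 1 − 0.1^(1/6) = 31.9% becomes 1 − 0.1^(1/5) = 36.9%. Detection at a true rate of 32% falls from 1 − 0.68^6 = 0.901 to 1 − 0.68^5 = 0.855.
- Pooled: 1 − 0.1^(1/24) = 9.15% becomes 1 − 0.1^(1/23) = 9.53%. Detection at 10% falls from 1 − 0.90^24 = 0.920 to 1 − 0.90^23 = 0.911.

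Under Section 10.3 the subject stays in the denominator, so the reported limit would still be the one for 6 or 24.

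**4. Outer case.** Suppose the lost subject would have had the only event of that type. The correct one-sided 90% Clopper-Pearson limit is then the p that solves (1 − p)^n + n·p·(1 − p)^(n−1) = 0.10. For n = 6 it is 51.0%, against 31.9% with no event. For n = 24 it is 15.3%, against 9.15%.

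**The case against.** The strongest answer is that the protocol already protects these subjects. Withdrawal is optional and is to be discussed with the sponsor. Section 5.6 brings forward the EOS assessments, which in Table 4 include AE review, safety laboratory tests, a pGSN sample and an antibody sample. Section 9.7 has no exception for withdrawn subjects in its recording window, and it presumes post-dose AEs to be related to study drug pending committee review, so an SAE would by default be followed beyond EOS. Section 9.6 follows AEs and significant laboratory abnormalities toward baseline. Section 10.3 keeps the subject in the analysis.

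Most of this stands, and it rules out four stronger readings that 7.11.1 may suggest on its own:

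- *Safety follow-up ends in the subjects with the most important events.* Not supported. The triggering event should be recorded, and a treatment-related SAE, or an AE recorded as the withdrawal reason, is followed.
- *Every unblinded subject has had a serious event.* Section 7.11.1 sets no seriousness or grade threshold. Section 5.1 also allows unblinding in the cohort safety review, where appropriate.
- *Everyone who decides on withdrawal knows the arm.* Section 7.11.1 does not say that the sponsor is told; the documentation is stored separately by the unblinded pharmacist.
- *The rule can only hide later events.* Some collection continues under 5.6 and 9.7.

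What the objection does not answer is the wording. The monitoring clause in 5.6 turns on the recorded reason, the 28-day contact turns on refusal, and 9.7 lets the EOS Visit close most AE follow-up while 5.6 moves the EOS assessments forward.

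**Conclusion.** The point holds in a limited form. Section 7.11.1 permits withdrawal from the study on a ground that gives no reason to stop collecting safety data, in subjects selected by a medical condition. The other sections largely secure the triggering event. They do not secure the remaining scheduled laboratory tests, the Day 28 antibody sample, new later events, or full follow-up of AEs that are neither treatment-related SAEs nor the recorded reason for withdrawal.

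The expected size is small, because individual unblinding should be rare in this study and withdrawal after it is discretionary; the documents give no frequency for either. The shifts from 31.9% to 36.9% at one dose level and from 9.15% to 9.53% pooled assume one lost treated subject who adds nothing for a later event type. Data up to withdrawal and the early EOS assessments would still count, so these are worst-case figures for one subject. The limits of 51.0% and 15.3% need the further assumption that this subject would have had the only such event. The case for the change rests on its low cost, not on a large expected bias.

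**What to change.** Replace the three withdrawal sentences in Section 7.11.1 (permission to withdraw, discussion with the sponsor, recording of date and reason) with:

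> Unblinding alone is not a reason for withdrawal from the study; unblinded subjects continue the remaining applicable safety, pGSN and antibody assessments through Day 28 unless a withdrawal criterion in Section 5.6 is met, and the unblinding is recorded and flagged in listings.

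All three must change together, since the second and third would contradict a new first sentence. The word applicable is needed because there is no Dose #5 profile if dosing has stopped. The reference to 5.6 keeps its other grounds for withdrawal.

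Then reconcile three sections with this text:

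- **5.6:** state where stopping treatment is meant and where leaving the study is meant. Its heading concerns treatment, but its list speaks of participation in the study and includes SAEs and Grade 3 or 4 AEs, so the exception above could otherwise reopen part of the gap. Say whether the 28-day contact also covers withdrawn subjects who do not refuse assessment.
- **9.6 and 9.7:** say whether EOS assessments brought forward count as the EOS Visit that closes AE follow-up, and align this with the recording window to 28 days after the last dose.

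Dosing decisions stay with the existing rules and are not touched. The cost is one replaced paragraph, some cross-references and the visits already scheduled for that subject. The downside is that later assessments in that subject are not blind, which the flag in the listings makes visible.
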